## Statistical Analysis Plan

Sponsor Name: Nitto Denko Corporation  
Sponsor Protocol ID: ND-L02-s0201-005

### 3.4.7 Laboratory Evaluations

The following hematology, serum chemistry, and urinalysis analytes recorded in the eCRF will be analyzed in this study. Absolute values will be compared to the laboratory reference range and classified as

- lower than reference range, clinically significant;
- lower than reference range, not clinically significant;
- normal in reference range;
- higher than reference range, not clinically significant;
- higher than reference range, clinically significant.

All values classified as high or low will be flagged on the listings. The baseline value will be defined as last scheduled or unscheduled value prior to the first dose of study treatment. Assessments carried out on day of first study treatment administration are considered to have taken place before the drug administration, if the corresponding times have not been recorded. For post-baseline, only data from scheduled visits will be included in the summary tables.

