## 6. Data Handling

### 6.1 Time points and Visit Windows

Day 1 is defined as the day of first dose of treatment (visit 2). Relative days after Day 1 are calculated as (assessment date – Day 1 date) + 1. Relative days prior to Day 1 are calculated as (assessment date – Day 1 date). The day prior to Day 1 is Day -1.

All data will be analyzed using nominal study visits as defined in the Study Schedule of Assessment and eCRF. Data collected at unscheduled visits will be listed only, except for the following:

- Data from unscheduled visits will be included in the calculation of baseline laboratory values.
- Data from unscheduled visits will be included in the calculation of the worst CTCAE grade or abnormality used in the laboratory shift tables.
- For a nominal visit with a missing measurement, the measurements of the unscheduled visits occurring between this particular visit and the two adjacent visits will be used to assign the analysis value. The closest unscheduled visit value that is not assigned to previous visits will be assigned to this nominal visit.

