#### 7.5.2 Secondary Efficacy Analysis

##### 7.5.2.1 Analyses of FVC

Values of FVC variables described in [Section 3.4.1](#) will be summarized with descriptive statistics by treatment arm and visit for the ITT Population. The summary will include FVC (or percent predicted FVC) values, the change and percentage change from baseline to each post-baseline visit for each parameter. Results from unscheduled visits will not be included in summary tables, but will be included in subject-level listings and statistical model.

A random coefficients model will be used to analyze the rate of decline in FVC (L) from baseline to Visit 14 (Day 169) as well as the absolute change from baseline in FVC at Visit 14 in the ITT Population. [REDACTED]

[REDACTED]

Reporting of model results will include the estimated mean change from baseline, adjusted for baseline FVC and standard of care, at each timepoint [REDACTED] with corresponding 95% CIs. In addition, mean slope (rates of change) of FVC from baseline to Visit 14 (Week 24) for each treatment arm will be estimated along with 95% CIs. Treatment differences between mean slopes and corresponding p-values will be presented. No adjustments for multiple comparisons will be made. Spaghetti plots of individual FVC (L) data over time will be produced for each treatment arm with estimated means from the random coefficient model and 95% CIs at each timepoint [REDACTED] superimposed.

Similar analysis will be repeated for FVC (L) relative change from baseline, absolute and relative change from baseline for percent predicted FVC (%FVC).

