### 7.5.2.2 Analyses of DLco

Values of DLco variables described in [Section 3.4.2](#) will be summarized with descriptive statistics by treatment arm and visit for the ITT Population. The summary will include the absolute and percent change from baseline to each post-baseline visit for each parameter. Results from unscheduled visits will not be included in summary tables or statistical models, but will be included in subject-level listings.

DLco corrected for hemoglobin and DLco not corrected for hemoglobin will be analyzed similarly as FVC as described in section 7.5.2.1.

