### 7.6.3 Laboratory Evaluations

All laboratory data will be reported in conventional units. Reference range will be presented in the listing. Out-of-reference-range values will be flagged as high (H) or low (L) in the listings.

Laboratory data will be summarized by treatment arm, overall, and visit using standard descriptive statistics for the SAF population. Changes from baseline will also be summarized.

For hematology and serum chemistry, shift tables presenting movement in and out of reference range from baseline to each scheduled post-baseline visit will be provided for each treatment arm.

[REDACTED]

- [REDACTED]
- [REDACTED]
- [REDACTED]

For subjects with abnormal baseline values, the following summary will also be created:

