## Statistical Analysis Plan

Sponsor Name: Nitto Denko Corporation  
Sponsor Protocol ID: ND-L02-s0201-005

- ALT or AST >2x Baseline or total bilirubin >1.5x Baseline
- ALT or AST >2x Baseline and a concomitant total bilirubin >2x Baseline
- If baseline measurements were <2.5x ULN: ALT or AST >5x baseline

For all subjects, number of subjects with elevated ALT or AST and Total Bilirubin following the Hy's Law (ALT or AST >3X ULN and Total Bilirubin >2X ULN) will be summarized. The onset date of ALT or AST elevation should be prior to or on the date of Total Bilirubin elevation. Additionally, Evaluation of Drug Induced Serious Hepatotoxicity (eDISH) plots will be generated for peak total bilirubin vs peak ALT and peak AST.

Box-plots of the absolute value of lab tests at each scheduled visit will be provided. All lab tests results will also be listed.

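### SAP rules on unscheduled data conflict: unscheduled liver peaks can fall out of laboratory summaries, and some Visit 14 lung values depend on which section is followed

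*SAP*

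**What the plan says.** **Laboratory data.** SAP 3.4.7 gives a rule with no exception or cross-reference: "For post-baseline, only data from scheduled visits will be included in the summary tables".

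SAP 6.1 sets a default for all data, "Data collected at unscheduled visits will be listed only, except for the following", followed by three exceptions. The first concerns laboratory baselines. The second reads "Data from unscheduled visits will be included in the calculation of the worst CTCAE grade or abnormality used in the laboratory shift tables". The third covers a missing measurement at a nominal visit and is not limited to any data type: "The closest unscheduled visit value that is not assigned to previous visits will be assigned to this nominal visit".

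For hematology and chemistry, the visible part of SAP 7.6.3 states that "shift tables presenting movement in and out of reference range from baseline to each scheduled post-baseline visit will be provided". It then plans counts of subjects with abnormal baselines whose ALT, AST or bilirubin exceeds multiples of baseline, a Hy's Law count (the "number of subjects with elevated ALT or AST and Total Bilirubin" above the usual limits), and eDISH plots of peak values. None of these says whether unscheduled draws count. A block between the shift tables and the liver counts is redacted.

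**Lung data.** For DLco, SAP 7.5.2.2 says "Results from unscheduled visits will not be included in summary tables or statistical models". SAP 7.5.2.3 has the same rule for HRCT. SAP 7.5.2.1 keeps unscheduled FVC out of the summary tables, but says such results "will be included in subject-level listings and statistical model".

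**The concern.** No section says which rule prevails. Two programmers could follow the SAP faithfully and produce different tables.

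For laboratory data the choice is not neutral. Unscheduled draws tend to be taken because something looks wrong, and protocol section 12 allows unscheduled assessments for subject safety. A rule that keeps only scheduled draws therefore tends to remove high values. The liver outputs are the ones most exposed, in a trial whose primary objective is safety.

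For DLco, HRCT and the FVC tables, the question is which subjects have a Visit 14 value at all. That should be fixed before unblinding and not left to programming.

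**Working it through.** The SAP gives no figure to reproduce here: section 2.3 states about 120 subjects, about 40 per arm, without power inputs. The check is a comparison of texts.

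**1. Shift tables.** Under 6.1, an unscheduled value worse than every scheduled one sets the subject's worst grade or abnormality. Under 3.4.7 it enters no post-baseline summary table. The shift tables visible in 7.6.3 run visit by visit, so the worst-grade table that 6.1 presupposes does not appear in the visible text.

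**2. Liver outputs.** The baseline-multiple counts, Hy's Law count and eDISH plots are not shift tables, so the worst-grade exception in 6.1 does not reach them.
- The counts are summaries, so both the 6.1 default and 3.4.7 apply.
- The eDISH plots are figures, so 3.4.7 does not strictly apply, but the 6.1 default does.
- The one remaining route in is the missed-visit fill-in. An extra draw taken between two attended visits does not qualify.
- The Hy's Law count also requires the ALT or AST elevation to start no later than the bilirubin elevation. Suppose ALT is raised only on an unscheduled draw between Days 57 and 85, and bilirubin is raised at Day 85. Dropping the extra draw can change whether the subject is counted.

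**3. A missed Visit 14 with an eligible unscheduled test.**

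| Endpoint | Following 6.1 | Following the endpoint's own section |
|---|---|---|
| DLco | value assigned to Visit 14 | not in tables or model (7.5.2.2) |
| HRCT | value assigned to Visit 14 | not in tables or model (7.5.2.3) |
| FVC, tables | value assigned to Visit 14 | not in tables (7.5.2.1) |
| FVC, model | used | used (7.5.2.1) |

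The FVC decline categories at Visit 14 are tabulated, so they are affected although the FVC model is not. Section 7.5.2.2 adds some doubt by also saying that DLco is analyzed like FVC.

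**4. Size.** One subject is 1/40 = 2.5% of an arm. The documents do not show how many unscheduled values will exist or how many will exceed all scheduled ones.

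**Illustration only.** Chemistry is listed on Days 29, 57, 85, 113, 141 and 169 (protocol section 12), each 28 days apart. If onset is random, an elevation lasting d days meets a scheduled draw with probability d/28. For assumed durations of 7, 14 and 21 days this is 7/28 = 25%, 14/28 = 50% and 21/28 = 75%. Visit windows of ±7 days are ignored. This shows why an unscheduled draw may be the only one on a peak; it does not measure what the table rule removes.

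**The case against.** **The laboratory rules can be reconciled.** Section 3.4.7 may be read as the default for by-visit tables, with 6.1 as the specific exception. Worst grades would then keep the unscheduled peaks. That is a sensible reading, but the SAP does not state it, and it does not reach the liver counts or eDISH plots.

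**The liver outputs look subject-based.** They count subjects, order elevations by onset date and plot peaks, which suggests that all values were intended. The text is silent, however, and the stated default points the other way.

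**Redaction.** The hidden block in 7.6.3 directly precedes the baseline-multiple counts and may contain a data rule. Much of protocol 8.4.5 on liver monitoring is also not visible. This stands, and it limits how firmly one can say that the liver outputs lack a rule. It does not remove the conflict between 3.4.7 and 6.1, or between 6.1 and 7.5.2.2.

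**Backstops.** A reader might infer that liver signals could vanish from the safety report. The documents do not support that. All laboratory results are listed with out-of-range values flagged, protocol 14.5 requires clinically relevant deterioration to be recorded as an AE, and the DMC reviews available safety laboratory data (protocol 7.4). The primary endpoints are TEAEs, treatment-emergent SAEs and discontinuations due to TEAEs, not laboratory tables.

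**The percentages.** A reader might take 25%, 50% and 75% as shares of peaks retained. They are not. A value is lost through the rule only if an unscheduled draw was taken and its exclusion changes the summary. A spike that nobody sampled is lost under any rule, and a repeat prompted by an abnormal scheduled draw follows an elevation already in the tables.

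**DLco.** A value reassigned under 6.1 could be regarded as no longer unscheduled. That would resolve the conflict, but the SAP does not say so. Modelling unscheduled FVC but not unscheduled DLco is a permissible choice and not in itself an error.

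**Conclusion.** The point holds, with medium confidence. Sections 3.4.7 and 6.1 conflict as written, and no order of precedence is given. On the literal default, an unscheduled ALT, AST or bilirubin peak is left out of the baseline-multiple counts, the Hy's Law count and the eDISH peaks unless it fills a missed visit. The loss is confined to laboratory summaries, and the redacted text in 7.6.3 may already address it. Separately, whether some subjects have a Visit 14 value for DLco, HRCT or the FVC tables depends on the section followed.

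The effect cannot be quantified beyond 2.5% of an arm per affected subject, assuming arms of about 40. It should be corrected because the affected liver outputs serve the primary objective and the remedy is simple.

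**What to change.** - **SAP 3.4.7 and 7.6.3:** state that by-visit summaries use nominal visits, including the 6.1 fill-in. State that worst-grade shifts, liver-threshold counts, the Hy's Law count and eDISH peaks use all post-baseline values, scheduled and unscheduled. If the redacted part of 7.6.3 already says this, a cross-reference in 3.4.7 is enough for the liver outputs.
- **SAP 6.1 and 7.5.2.1 to 7.5.2.3:** state that the fill-in for a missed visit prevails, and that each value enters an analysis only once, so that a filled-in value is not also used at its actual day.
- **Left to the sponsor:** whether other unscheduled DLco or HRCT values enter the models. The SAP need only state the choice.

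The cost is a few sentences of SAP text and minor programming, with no new data. It should be done before unblinding.

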## Statistical Analysis Plan

Sponsor Name: Nitto Denko Corporation  
Sponsor Protocol ID: ND-L02-s0201-005

the corresponding times have not been recorded. For post-baseline, only data from scheduled visits will be included in the summary tables.

### 3.4.9 Physical Examination

Complete and abbreviated physical examinations will be evaluated in this study. A complete physical examination includes general appearance, eyes/ears/nose/throat/head/neck, chest and lungs (including inspection of the thorax for scars consistent with surgical lung biopsy at Screening), cardiovascular, abdomen, musculoskeletal, lymphatic, dermatologic, neurologic, psychiatric, and extremities. An abbreviated physical exam includes general appearance, nose/throat, jugular venous distension (sitting; absent or present), auscultation of the lungs (anterior/posterior, 4 quadrants; wheezes, crackles, rhonchi [absent or present], other sounds [describe]), auscultation of the heart, lower extremity venous distention (absent or present), pitting edema (0, 1+, 2+, 3+, or 4+). Any clinically significant abnormal result after baseline should be recorded as an AE.

### 3.4.10 12-Lead Electrocardiograms

The following quantitative ECG measurements will be taken during the study:

- heart rate (bpm);
- RR interval (msec);
- PR interval (msec);
- QRS interval (msec);
- QT interval (msec);
- Fridericia's corrected QT (QTcF) interval (msec).

An overall investigator assessment of ECG will be provided (categories "normal", "abnormal, not clinically significant" and "abnormal, clinically significant"). Clinically significant changes not already noted or significantly worsened than documented in Medical History will be recorded as AEs.

The baseline value will be defined as last scheduled or unscheduled value collected prior to start of study treatment. Assessments carried out on day of first study treatment administration are considered to have taken place before the drug administration, if the corresponding times have not been recorded. For post-baseline, only data from scheduled visits will be included in the summary tables. When triplicate ECG tracings are obtained at a study visit or timepoint, the triplicate average (or if fewer, average of ECGs available) will be included in the analysis.

### 3.4.11 Other Safety Assessments

The following other safety assessments will be performed:

**Statistical Analysis Plan**

Sponsor Name: Nitto Denko Corporation  
Sponsor Protocol ID: ND-L02-s0201-005

[REDACTED]

[REDACTED]

[REDACTED]

- [REDACTED]  
[REDACTED]  
[REDACTED]
- [REDACTED]  
[REDACTED]  
[REDACTED]  
[REDACTED]
- [REDACTED]  
[REDACTED]  
[REDACTED]  
[REDACTED]

[REDACTED]

[REDACTED]

[REDACTED]

[REDACTED]

[REDACTED]

[REDACTED]

[REDACTED]

[REDACTED]

[REDACTED]

[REDACTED]

[REDACTED] [REDACTED]	[REDACTED]
[REDACTED]	[REDACTED]
[REDACTED]	[REDACTED] [REDACTED]
[REDACTED]	[REDACTED]
[REDACTED]	[REDACTED] [REDACTED] [REDACTED]
[REDACTED]	[REDACTED] [REDACTED]
[REDACTED]	[REDACTED]

**Statistical Analysis Plan**

Sponsor Name: Nitto Denko Corporation  
Sponsor Protocol ID: ND-L02-s0201-005

[REDACTED]

[REDACTED]	[REDACTED]

[REDACTED]

[REDACTED]

## 5. Analysis populations

### 5.1 Safety Population (SAF)

The safety population (SAF) will include all subjects who receive at least 1 dose of study treatment. Subjects will be analyzed according to the study treatment they actually received.

### 5.2 Intent-to-treat Population (ITT)

The ITT population will include any randomized subjects with treatment assignment according to the planned randomization.

### 5.3 Pharmacokinetic Population 1 (PK1)

PK population 1 will include subjects in the PK subset who receive at least 1 dose of study treatment and have a majority of scheduled PK samples drawn for serial PK measurements that allow for PK parameters to be generated. A majority of samples is defined by sampling to at least 4 hours after end of infusion. Subjects who do not complete the study treatment infusion (Visit 2) will be excluded from the PK analysis.

### 5.4 Pharmacokinetic Population 2 (PK2)

PK population 2 will include subjects who have at least 3 of the 7 planned trough samples collected for subjects in the PK subset and both 2 planned trough samples collected for non-PK subjects to allow for a comparison of trough levels across dosing weeks.

### 5.5 Per Protocol Population (PP)

The per protocol population (PP) will exclude non-evaluable subjects and subjects with important protocol deviations thought to impact the ability to assess the effect of study treatment.

Evaluable subjects are defined as subjects who received at least one dose of study treatment (not including pre-medication) and have baseline and at least one post baseline FVC or have baseline and at least one post baseline DLco.

Non-evaluable subjects are subjects who do not meet the evaluable criteria.

Protocol deviations are defined as any change, divergence, or departure from the study design or procedures defined in the study protocol. Important protocol deviations are a subset of protocol deviations that may significantly impact the correctness, accuracy, and/or completeness of the study data or that may significantly affect a subject's rights, safety, or well-being.

## Statistical Analysis Plan

Sponsor Name: Nitto Denko Corporation  
Sponsor Protocol ID: ND-L02-s0201-005

## 6. Data Handling

### 6.1 Time points and Visit Windows

Day 1 is defined as the day of first dose of treatment (visit 2). Relative days after Day 1 are calculated as (assessment date – Day 1 date) + 1. Relative days prior to Day 1 are calculated as (assessment date – Day 1 date). The day prior to Day 1 is Day -1.

All data will be analyzed using nominal study visits as defined in the Study Schedule of Assessment and eCRF. Data collected at unscheduled visits will be listed only, except for the following:

- Data from unscheduled visits will be included in the calculation of baseline laboratory values.
- Data from unscheduled visits will be included in the calculation of the worst CTCAE grade or abnormality used in the laboratory shift tables.
- For a nominal visit with a missing measurement, the measurements of the unscheduled visits occurring between this particular visit and the two adjacent visits will be used to assign the analysis value. The closest unscheduled visit value that is not assigned to previous visits will be assigned to this nominal visit.

### 6.2 Handling of Dropouts, Missing Data, and Outliers

Missing values on FVC, DLCO and DLCO corrected for hemoglobin, HRCT analysis variables, [REDACTED] at Visit 14 (Day 169) will not be imputed. In situations where the efficacy endpoints are missing, all available data will be analyzed with a mixed-effects model for repeated measures (MMRM). To evaluate robustness of results, sensitivity analyses will be performed by imputing missing data using statistical modelling of available data.

Incomplete dates (partial or missing dates) for start date of AEs will be imputed and used to determine treatment-emergent status as follows:

- If the start date of an AE is completely missing, the first dosing date (Day 1) and time will be used for the imputation and the AE will be considered treatment-emergent.
- If the start date of an AE is missing day and month:
  - If the year of the AE start date is the year of the first dosing date, the month and day will be imputed using the month and day of first dosing date;
  - Otherwise, the month and day will be imputed as January 1.
- If the start date of an AE is missing the day only:

## Statistical Analysis Plan

Sponsor Name: Nitto Denko Corporation  
Sponsor Protocol ID: ND-L02-s0201-005

- If the year and month of the AE start date is the same as the year and month of the first dosing date, the day will be imputed using the day of first dosing date;
- Otherwise, the day will be imputed as the first day of the month.
- If an imputed AE start date is later than the corresponding AE end date, the imputed AE start date will be replaced with the AE end date.

AEs with missing relationship (related or not related) to study treatment will be treated as related AEs in summaries of AEs by relationship to study treatment.

Partial dates with day or day and month missing for concomitant medications date will be imputed as follows:

- If the year and month are present and the day is missing, set the start date as the first day of the month, and set the end date as the last day of the month as applicable.
- If the year and day are present and the month is missing, set the month to January as the start date, and set month to December as the end month as applicable.
- If the year is present and the month and day are missing, set January 1 as the start date, and set December 31 as the end date as applicable.
- Completely missing dates will not be imputed.
- If the start date is completely missing and the end date is on or after the first dosing date, the medication will be classified as concomitant; if the end date is missing, the medication will be classified as ongoing. Medications for which both the start and end dates are missing will be classified as concomitant.

## 7. Statistical Methods

### 7.1 General Principles

Efficacy data will be summarized and analyzed on the ITT population and PP population. Safety and treatment compliance data will be summarized based on the SAF population. Demography and other baseline characteristics data will be summarized based on the SAF population.

Baseline is defined as the last scheduled or unscheduled value assessed on or before study day 1, prior to the first dose of study treatment, including pre-medication unless otherwise indicated. Assessments carried out on day of first dose administration are considered to have taken place before the dose administration, if

